8.4 TREATMENT OF OVERDOSE

Study treatment overdose is the accidental administration of a drug in a quantity that is higher than the assigned dose. An overdose or incorrect administration of study treatment is not an AE unless it results in untoward medical effects (see Sections 5 and 5.2 of [Appendix 2](#) for further details).

Decisions regarding dose-interruptions or modifications (if applicable) will be made by the Investigator in consultation with the Medical Monitor based on the clinical evaluation of the participant.

In the event of an overdose, the Investigator should:

1. Contact the Sponsor’s Medical Monitor immediately.
2. Closely monitor the participant for AE/SAE and laboratory abnormalities until resolved.
3. Document the quantity of the excess dose in the eCRF.

8.5 PHARMACOKINETICS

Mandatory blood samples to evaluate serum concentrations of RO7049665 will be collected at on-treatment visits as specified in the SoA (see Section 1.3). The date and time of each sample collection will be recorded in the eCRF. Serum concentrations of RO7049665 will be measured by specific and validated enzyme-linked immunosorbent assay methods.

During the course of the study, PK sampling timepoints may be modified on the basis of emerging data to ensure the PK of RO7049665 can be adequately characterized. Additional PK samples will be taken at the time of treatment discontinuation, if the participant experiences an injection-related AE (such as an IRR).

- Placebo-treated participants may not be analyzed in the first instance, but retained for subsequent analysis if appropriate.
- If required, remaining PK samples, or any remaining volume of blood samples, may also be used for assay development/validation experiments and ADA characterization.

The PK samples will be destroyed 5 years after the date of final clinical study report (CSR). Details on sampling procedures, sample storage, and shipment are given in the sample documentation.

Genetic analyses will not be performed on these samples unless consent for this was included in the informed consent. Participant confidentiality will be maintained.

Drug concentration information that may unblind the study, will not be reported to investigative sites or blinded personnel until the study has been unblinded.

For participants who consent to RBR, leftover samples will be transferred to RBR (see Section 8.9).

8.6 IMMUNOGENICITY ASSESSMENTS

As RO7049665 is a fusion protein that consists of two human IL-2 muteins covalently linked to a human monoclonal antibody there is a risk that ADAs could develop (see Section 2.3).

The date and time of each sample will be recorded in the eCRF. Additional samples will be taken in participants with clinical signs of hypersensitivity reaction for ADA evaluation (see SoA Section 1.3). In each case, for each collected ADA sample, a corresponding PK sample will be collected at the same timepoint for the determination of the RO7049665 concentration.

Validated ADA assays will be employed to detect ADAs against RO7049665 (in serum). Samples which are positive for ADA will be further characterized and their neutralizing capability for endogenous IL-2 will be assessed using the neutralizing antibody assay.

If required, remaining ADA samples may also be used for assay development/validation experiments, further ADA characterization, for compound-related exploratory analyses, or to help develop further blood tests, after they are used for the mentioned intended uses. For exploratory purposes, such as epitope characterization or IgG-IgM-isotyping, samples may be analyzed by assays which are not fully validated.

The ADA serum samples will be destroyed 5 years after the date of final CSR. For participants who consent to RBR, leftover samples will be transferred to RBR (see Section 8.9).

Samples from placebo-treated participants may not be analyzed in the first instance but may be retained for subsequent analysis if appropriate.

Details on sampling procedures, sample storage, and shipment are documented in the sample documentation.

8.7 PHARMACODYNAMICS AND BIOMARKERS ANALYSES

A fit for purpose biomarker strategy (Section 4.2.3) will be implemented, monitoring several key biomarker types.

Systemic PD will be assessed in the expected target cell population (T_{regs}), with the aim of reconfirming and further characterizing the dose-dependent effects of the drug in this study population. For consistency, the same technology as in prior clinical studies (flow cytometry) will be employed. In addition to the desired selective expansion of target cells, changes in other cell types of interest (including but not limited to T_{effs} , NK cells, T_{fhs} , B cells) will be monitored, thereby corroborating the mode of action (MoA) and potentially informing dose selection and clinical response.

When possible (paired baseline and on-treatment liver biopsies available), liver tissue changes in regulatory and effector T cells will also be measured. This will enable the assessment of tissue PD effects, their comparison with systemic PD observations as well as a preliminary evaluation of intrahepatic T_{reg}/T_{eff} ratio as a response predictive biomarker. Tissue infiltrating lymphocytes will most likely be assessed by immunohistochemistry (IHC), given the availability of historical liver biopsies at baseline, as opposed to fresh samples amenable for flow cytometry. In addition, (spatial) gene expression analyses (targeted genes or whole transcriptome) may be performed on liver biopsy-derived material for enhanced insights into MoA and activated pathways.

Select exploratory serum and/or plasma disease biomarkers will be tested for their diagnostic (e.g., auto-antibodies, anti-nuclear antibodies [ANA], smooth muscle

antibodies (SMA), LKM-1, anti-LC1, anti-SLA/LP, anti-LC1, anti-LKM3) ([Galaski et al. 2020](#)) or progression monitoring value (e.g., IgG, IgA, IgM).

Several soluble PD markers will be monitored, including but not limited to, sCD25, cytokines either mechanistically linked to the study treatment MoA (IL-5, IL-6, IL-10, TNF- α , and potential others) as well as cytokines or chemokines hypothesized to either have patient stratification potential (e.g., baseline IL-2) or an ability to be used as non-invasive response to treatment markers (e.g., CXCL10).

Non-invasive markers of liver fibrosis and steatosis will also be measured in the periphery to support MoA and provide supportive evidence for their use as surrogate liver function assessments. These may include but are not limited to composite scores of liver fibrosis.

Additional PD biomarkers and methods to obtain further confidence on the mechanism of action of RO7049665 in participants may be tested, including but not limited to epigenetic signatures of T-cell subsets, e.g., T cell-specific demethylation region.

8.7.1 Genetic and Genomic Analyses

8.7.1.1 Clinical Genotyping

A mandatory whole blood sample will be taken for DNA extraction from every participant in all countries where this assessment is permitted (see SoA Section [1.3](#)).

The DNA may be used for, but analysis is not limited to:

- Genetic variants of the IL-2 gene or other genes encoding proteins involved in IL-2 mediated signal transduction.
- Genetic variants of pathways related to AIH or other autoimmune diseases.
- Genes coding for human leukocyte antigens (i.e., HLA gene family).

Data arising from all biosamples, including samples for analyses of inherited DNA, will be subject to the confidentiality standards described in Section 1.4, [Appendix 1](#). For participants who consent to RBR, leftover samples will be transferred to RBR (see Section [8.9](#)).

8.8 PHARMACODYNAMICS AND BIOMARKER SAMPLES

Samples will be collected for biomarker assessments at the time points specified in the Schedules of Activities (Section [1.3](#)). Biomarkers will be evaluated as described in Section [8.7](#).

The samples may also be used for research purposes to identify biomarkers useful for predicting and monitoring response to and safety of RO7049665, assess PD effects of

RO7049665, and investigate mechanism of therapy resistance. Additional markers may be measured in the case that a strong scientific rationale develops.

Based on continuous analysis of the data in this study and other studies, any sample type and/or analysis not considered to be critical for safety may be stopped at any time if the data from the samples collected does not produce useful information.

Unless otherwise specified below, samples (including blood, slides, extracts, etc.) will be destroyed no later than 5 years after the final CSR. For participants who consent to RBR, leftover samples will be transferred to RBR (Section 8.9).

Any remaining blood/tissue, or appropriate, sample type after the specified analyses may also be used for additional (assay) validation experiments. Samples may be used for research to develop methods, assays, prognostics and/or companion diagnostics related to IL-2, T cell subsets and autoimmune diseases.

Details on processes for collection and shipment of these samples can be found in separate sample documentation.

8.8.1 Mandatory Samples

The following samples for PD and biomarker research are required and will be collected from all participants:

8.8.1.1 Blood Sampling

Blood samples will be collected for the following assessments:

- To quantify relative and absolute WBC counts (T cells, B cells, NK cells, eosinophils) by flow cytometry as well as to complete white blood count differential. Tests may include (but are not limited to) markers for quantification and characterization of T_{reg} and T_{eff} cell subsets CD3, CD4, CD8, CD25, CD127 and FoxP3.
- A mandatory whole blood sample will be taken for DNA extraction and clinical genotyping from every participant. If the sample is missed on Day 1, it can be collected at any other scheduled visit.

8.8.1.2 Tissue Sampling

A fresh or historical liver biopsy is required prior to baseline. Provided no worsening of disease has occurred, a historical biopsy taken no more than 12 months prior to randomization is acceptable. If a FFPE block is available, it is mandatory to provide it to the Sponsor. An optional liver biopsy sample will be taken at 6 months after treatment initiation.

The purpose is to conduct the following assessments:

- Characterization of infiltrating WBCs by histology (hematoxylin and eosin-staining) and immunohistochemistry (IHC). IHC markers tested may include but are not limited to CD3, CD4, CD8, and FoxP3.

- RNA extraction on biopsy samples may be performed in order to undertake optional whole or targeted transcriptome gene expression analysis with or without spatial resolution.
- Methylation signature changes induced by the study treatment indicative of quantitative and specific changes of T-cell subsets may be assessed.

8.8.1.3 Serum and Plasma Samples

Serum and plasma samples will be collected for the following assessments:

- To measure cytokines mechanistically linked with the study treatment's mode of action. Soluble biomarkers considered for testing include, but are not limited to IL-5, IL-6, IL-10.
- To measure cytokines or chemokines with stratification (baseline IL-2) or treatment response potential (CXCL10).
- To measure disease biomarkers including but not limited to auto-antibodies (e.g. ANA, SMA) or immunoglobulins (e.g., IgG, IgA, IgM).
- To measure non-invasive markers of liver fibrosis, e.g. but not limited to: α -2-macroglobulin, haptoglobin, apolipoprotein A1, hyaluronic acid, procollagen III amino-terminal peptide (PIIINP), and tissue inhibitor of matrix metalloproteinase 1 (TIMP-1).
- Additional soluble biomarkers to obtain further confidence on mechanism of action of RO7049665 in humans, PD or disease markers may also be tested.

8.8.1.4 Optional Samples

An optional liver biopsy may be taken (see Section [8.8.1.2](#)).

The ICF will contain a separate section with a separate signature field that addresses the use of optional samples.

8.9 SAMPLES FOR RESEARCH BIOSAMPLE REPOSITORY

8.9.1 Overview of the Research Biosample Repository

The Roche RBR is a centrally administered group of facilities for the long-term storage of human biologic samples, including body fluids, solid tissues, and derivatives thereof (e.g., DNA, RNA, proteins, peptides). The collection, storage and analysis of the RBR samples will facilitate the rational design of new pharmaceutical agents and the development of diagnostic tests, which may allow for individualized drug therapy for patients in the future.

Collected RBR samples will be used to achieve the following objectives:

- To study the association of biomarkers with efficacy or progressive disease.
- To identify safety biomarkers that are associated with susceptibility to developing AEs or can lead to improved AE monitoring or investigation.

- To increase knowledge and understanding of disease biology and drug safety.
- To study treatment response, including drug effects and the processes of drug absorption and disposition.
- To develop biomarker or diagnostic assays and establish the performance characteristics of these assays.

8.9.2 Sample Collection

The following samples will be stored in the RBR and used for research purposes, including, but not limited to, research on biomarkers related to RO7049665, diseases or drug safety:

- Leftover plasma samples
- Leftover serum samples
- Leftover blood samples
- Leftover liver tissue samples
- Leftover blood samples for DNA extraction
- Leftover PBMCs prepared from blood

Samples collected for DNA extraction include, but is not limited to, genomic analysis and may be sent to one or more laboratories for analysis of germline or somatic mutations via whole genome sequencing (WGS), whole exome sequencing (WES), next-generation sequencing, or other genomic analysis methods like spatial transcriptomics or other methods developed in the future.

Genomics is increasingly informing researcher's understanding of disease pathobiology. WGS provides a comprehensive characterization of the genome and, along with clinical data collected in this study, may increase the opportunity for developing new therapeutic approaches. Data will be analyzed in the context of this study but may also be explored in aggregate with data from other studies. The availability of a larger dataset will assist in identification of important pathways, guiding the development of new targeted agents.

Participants will not be identified by name or any other personally identifying information. Data generated from RBR samples will be analyzed in the context of this study but may also be explored in aggregate with data from other studies. The availability of a larger dataset will assist in identification and characterization of important biomarkers and pathways to support future drug development.

For all samples, dates of consent and sample collection should be recorded on the associated RBR page of the eCRF. Details on processes for collection and shipment of these samples can be found in separate sample documentation.

RBR samples will be stored and used until no longer needed or until they are exhausted. The RBR storage period will be in accordance with the IRB/IEC-approved Informed Consent Form and applicable laws (e.g., Health Authority requirements).

The repository samples will be subject to the confidentiality standards (as described under Confidentiality and in [Appendix 1](#)).

8.10 MEDICAL RESOURCE UTILIZATION AND HEALTH ECONOMICS

For Health Economics/Medical Resource Utilization and Health Economics parameters see Section [8.1.1.1](#).

8.11 TIMING OF STUDY ASSESSMENTS

8.11.1 Screening and Pre-treatment Assessments

Written informed consent for participation in the study must be obtained before performing any study-specific screening tests or evaluations. Informed Consent Forms (ICFs) for enrolled participant and for participants who are not subsequently enrolled will be maintained at the study site.

All screening, and all pre-treatment assessments (related to entry criteria), must be completed and reviewed to confirm that participants meet all eligibility criteria. The Investigator will maintain a screening log to record details of all participants screened and to confirm eligibility or record reasons for screening failure.

An Eligibility Screening Form documenting the Investigator's assessment of each screened participant with regard to the protocol's inclusion and exclusion criteria is to be completed by the Investigator and kept at the investigational site.

Screening and pre-treatment assessments will be performed within 28 days prior to Day 1, unless otherwise specified.

8.11.2 Assessments during Treatment

Under no circumstances will participants who enroll in this study and have completed treatment as specified, be permitted to be allocated a new randomization number and re-enroll in the study.

All assessments must be performed as per SoA (Section [1.3](#)). Assessments scheduled on the day of study treatment administration should be performed prior to administration of study treatment, unless otherwise noted in the SoAs. COAs (Section [8.1.1](#)) should be performed prior to the completion of other study assessments.

8.11.3 Assessments at Study Completion/Early Termination Visit

Participants who complete the study (defined as relapse) or discontinue from the study early will be asked to return to the clinic 28 days \pm 3 days after the final dose of study treatment for a follow-up visit.

8.11.4 Follow-Up Assessments

After the follow-up visit, AEs should be followed as outlined in the SoA (Section 1.3) and in Sections 8.3.1 and 8.3.3.

8.11.5 Assessments at Unscheduled Visits

For activities that are required to be performed in case of an unscheduled visit, refer to the SoA (Section 1.3).

9. STATISTICAL CONSIDERATIONS

9.1 STATISTICAL HYPOTHESES

The hypothesis associated with the primary estimand (see Section 3.1) for this study is that the hazard ratio (HR) for the risk of relapse in the 7.5 mg RO7049665 compared with that of placebo is less than 1. In other words, that 7.5 mg RO7049665 increases the time to relapse following forced tapering of CCS/ \pm NSI therapy in participants with confirmed AIH who have been in stable biochemical remission for at least two years (*or less if according to the local practice*) and on stable AIH treatment for *at least 3 months prior to randomization (and who have not had a dose increase 6 months prior to randomization)*.

Six months after the start of CCS tapering, the relapse rate on placebo is assumed to be 45% (van Gerven 2013). It is estimated that treatment with RO7049665 will reduce the relapse rate to 15%. Under the assumption of exponential times to relapse, these six-month relapse rates imply mean times to relapse of 10.0 months in the placebo arm and 36.9 months in the treatment arm, leading to a reference hazard ratio of 0.272.

The hypotheses formally tested in this study are

$$H_0: HR = 1 \text{ vs } H_1: HR < 1$$

9.2 SAMPLE SIZE DETERMINATION

The sample size for this study is based on independent pairwise comparisons of each RO7049665 group—i.e., high dose (7.5 mg) and low dose (3.5 mg) with placebo. The total sample size required is obtained by multiplying the appropriate per-group size by three. Methods for the control of the family-wise error rate are described both in this section and in Section 9.3.

The reference treatment effect is 0.272. The study will use an overall one-sided type 1 error rate (significance level) of 2.5%. A power of 90% against the reference treatment effect is required.

There will be one opportunity to stop for success before the end of the study, at 50% information. An O'Brien-Fleming-like alpha-spending rule will preserve the type 1 error rate. The success boundary will be binding.

There will be two opportunities to stop for futility before the end of the study: once at 25% information (i.e., when 25% of the maximum number of events have occurred) and once at 50% information (i.e. when 50% of the maximum number of events have occurred). A Pocock-like beta-spending rule will preserve power of the study. The futility boundary will be non-binding.

If the proportional hazards assumption holds, these assumptions imply that 29.1 events (i.e., 30 events for all practical purposes) in the placebo and 7.5 mg RO7049665 arms combined are required to achieve the desired power and significance levels.

Under the assumption that recruitment to the study will take approximately 19 months, that sites will be activated at uniform rate for six months, after which recruitment will plateau, and that follow-up should continue for at most 6 months after the last patient to enter the study is randomized, then recruitment of 28 participants per arm will generate the required number of events.

Table 9 Summary of the Group Sequential Design

Stage	Interim 1	Interim 2	End of study
Information rate	25%	50%	100%
Efficacy boundary (z-value scale)	∞	2.963	1.969
Futility boundary (z-value scale)	-0.046	0.738	
Number of subjects ^{a,c}	31	47	56
Cumulative number of events ^a	7.3	14.5	29.1
Analysis time ^{b,c}	11.7	16.3	25.0
Cumulative alpha spent	<0.0001	0.0015	0.025
Cumulative power	<0.0001	0.3159	0.9000
One-sided local significance level	N/A	0.0015	0.0245 ^d
Efficacy boundary (t)	N/A	0.211	0.482
Futility boundary (t)	1.035	0.679	
Overall exit probability (under H0)	0.4815	0.3136	
Exit probability for efficacy (under H0)	<0.0001	0.0015	
Exit probability for efficacy (under H1)	<0.0001	0.3159	
Exit probability for futility (under H0)	0.4815	0.3121	

- a: For the two arms (the placebo arm and one of the RO7049665 arms) in question.
- b: Months after FPFV.
- c: Estimate.
- d: The hazard ratio that gives rise to a p-value of 0.0245 at the end of study analysis is approximately 0.594. This is the minimum detectable difference for the study and, assuming a mean time to relapse of 10.0 months in the placebo arm, corresponds to a mean time to relapse of 16.9 months on RO7049665.

Thus, the study is expected to recruit $3 \times 28 = 84$ participants in total and run for no longer than 25 months from FPFV to LPLV. If the enrolment rate or event rate differ from the assumptions used in these calculations, then either the number of participants or the duration of follow-up (or both) may be varied in order to ensure that the required number of events is observed.

Sample size calculations were performed using R package version 2.0.6 ([Wassmer and Pahlke, 2019](#)). Details are filed in the study electronic Trial Master File (eTMF).

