4.1.2 Stopping-rules Criteria

The study will stop if either of the interim analyses recommends stopping for success. If any interim recommends stopping for futility, the Sponsor's project team will make the actual decision whether to stop or continue the study. This process is mandated by the binding nature of the success boundary and the non-binding nature of the futility boundary defined in Section 9.2. Reasons for continuing the study after a futility recommendation could include, but are not limited to, an efficacy effect that is smaller than assumed in the sample size calculation but still of clinical relevance, or evidence of potential benefit not considered in the primary efficacy analysis.

The dosing in the study will be suspended if any of the conditions below occur in participants treated with RO7049665:

- Clinically manifest secondary (reactive) hypereosinophilia (HER) in > 3 participants.
- Grade 3 hypersensitivity reaction (as per National Cancer Institute Common Terminology Criteria for Adverse Events [NCI-CTCAE] v. 5.0) in > 1 participant considered related to RO7049665.
- Local ISRs leading to treatment discontinuation in > 5 participants, considered related to RO7049665.
- ADA with neutralizing potential against endogenous IL-2 in ≥ 1 participant.
- Other findings (e.g., presence of clinically manifest safety findings in treatment arms typically associated with therapeutic IL-2 doses as per aldesleukin label, other AEs or lab abnormalities) that, at the joint discretion of the Sponsor's lead clinical scientist and safety science leader, the Sponsor's IMC and the Investigators, indicate that dosing should be stopped.

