9.3 MULTIPLICITY

There are three sources of multiplicity in this study: multiplicity due to interim analyses, multiplicity due to multiple doses, and multiplicity due to multiple endpoints.

The overall type 1 error rate for the study is protected against multiplicity due to interim analyses, because of the alpha- and beta-spending rules described in the preceding section.

The overall type 1 error rate for the study will be protected against multiplicity due to multiple doses by using a step-down, or gatekeeper, procedure. The statistical significance of the difference in response between the 3.5 mg RO7049665 group and the placebo group will be assessed if and only if the corresponding difference between the 7.5 mg RO7049665 and placebo has already been shown to be statistically significant.

The study has a single primary endpoint, corresponding to the single primary estimand. All other endpoints are secondary or exploratory. Therefore, no adjustment to nominal p-values will be made to protect the overall type 1 error rate for the study against multiplicity of endpoints.

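### The 90% power in Section 9.2 is delivered only for 7.5 mg versus placebo; the step-down 3.5 mg test has no stated boundary and lower power, about 72% to 83% at the planned event count

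*Combined protocol and SAP*

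**What the plan says.** Section 9.2 opens with "The sample size for this study is based on independent pairwise comparisons of each RO7049665 group", naming both doses, and obtains the total by multiplying the per-group size by three. It continues: "The reference treatment effect is 0.272", "The study will use an overall one-sided type 1 error rate (significance level) of 2.5" per cent, and "A power of 90% against the reference treatment effect is required". Section 9.1 supplies the rates: at six months "the relapse rate on placebo is assumed to be 45" per cent, against 15% on RO7049665, with no separate figure for the lower dose. The 29.1 events are stated for placebo and 7.5 mg combined. Footnote a to Table 9 is wider, attaching the event and subject counts to either pair: "For the two arms (the placebo arm and one of the RO7049665 arms) in question".

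Three other sections govern how 3.5 mg is tested:
- Section 9.3: the 3.5 mg comparison "will be assessed if and only if the corresponding difference between the 7.5 mg RO7049665 and placebo has already been shown to be statistically significant".
- Section 9.6: the looks are tied to events in the 7.5 mg and placebo arms, and approximated by 12, 23 and 45 events in the whole study.
- Section 4.1.2: "The study will stop if either of the interim analyses recommends stopping for success". That boundary is binding; the futility boundary is not.

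Section 9.5.2.2 says that secondary endpoints will not be formally tested. Table 5 lists 3.5 mg versus placebo as a secondary objective.

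**The concern.** Table 9 describes a two-arm trial that runs its own course to its own boundary. The 7.5 mg comparison does that. The 3.5 mg comparison does not: it uses the same placebo patients, is tested only when 7.5 mg succeeds, and loses its remaining follow-up if 7.5 mg wins at Interim 2, at about 14.5 pair events. The 90% therefore cannot carry over to it. The plan also gives no critical value for 3.5 mg at either look, so that value could be chosen after the result is known.

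The stake is the interpretation of the lower dose. If 7.5 mg wins early and 3.5 mg misses, a reader who takes the trial to have 90% power for each dose would count the miss as evidence against 3.5 mg, when it may reflect only a curtailed test.

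**Working it through.** **Inputs.** Six-month relapse 45% and 15% (Section 9.1). One-sided 2.5%, 90% power, 29.1 pair events, looks at 25%, 50% and 100% information, efficacy z of none / 2.963 / 1.969, futility z of -0.046 / 0.738 (Section 9.2 and Table 9). Assumed, because the documents do not say: hazard ratio 0.272 for both doses, and correlation 0.5 between the two test statistics (one shared arm, equal allocation). Patient-level simulation gave correlations of 0.44 to 0.53.

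**1. The plan's own figure.**
- Hazard ratio = ln(0.85)/ln(0.55) = 0.272.
- Final drift (Schoenfeld) = |ln 0.272| × √29.1 / 2 = 3.51.
- Simulating this process with the Table 9 boundaries and futility obeyed gives 31.6% success at Interim 2 (stated 31.59%) and 90.0% overall (stated 90.00%).
- A stand-alone 3.5 mg comparison would also have 90.0%. Table 9 is correct as a two-arm design.

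**2. The 3.5 mg test as the plan runs it.** The two z-processes are simulated jointly; 3.5 mg is tested only at the look where 7.5 mg succeeds. With the Table 9 boundaries for both doses:
- 7.5 mg stops at Interim 2 in 31.6% of trials, and 3.5 mg then exceeds 2.963 in 53.6% of them: 0.316 × 0.536 = 0.169.
- 7.5 mg succeeds at the end in 90.0 - 31.6 = 58.4%, and 3.5 mg then exceeds 1.969 in about 94.1%: 0.584 × 0.941 = 0.550.
- Sum: 0.719.

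**3. Dependence on the unspecified boundary** (futility obeyed):

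| 3.5 mg boundary (Interim 2 / final) | 29.1 pair events | 45 total events (about 34 pair) | HR 0.40 for 3.5 mg, 29.1 events |
|---|---|---|---|
| 2.963 / 1.969 (Table 9) | 72% | 76% | 47% |
| 2.157 / 2.201 (Pocock-type) | 79% | 85% | 52% |
| 1.96 / 1.96 (uncorrected) | 83% | 87-88% | 60% |

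The 45-event trigger gives more than 30 pair events because most relapses fall on placebo. If both doses work equally well, 45 total and 34.1 pair events imply 45 - 34.1 = 10.9 events per active arm and 23.2 on placebo.

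**4. Other sensitivities.** With Table 9 boundaries and 29.1 events, ignoring futility gives 75%; correlation 0.7 gives 76% and correlation 0 gives 65%. Patient-level log-rank simulation gives 72.2% at 8/15/30 pair events and 75.6% at the 12/23/45 triggers.

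**5. False positives for 3.5 mg.** With 3.5 mg null, 7.5 mg at 0.272 and futility ignored, 1.96 at either look gives about 2.85%, above the 2.5% that Section 9.3 says is protected. The Pocock-type boundary gives about 1.7%.

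**6. Where the loss comes from.** Compared like for like, the step-down rule alone costs 93.9 - 89.4 = 4.5 points with no interims. With interims and futility, and 3.5 mg followed to the end, it costs 90.0 - 85.9 = 4.1 points. The early stop takes a further 85.9 - 71.9 = 14.0 points with Table 9 boundaries, but only about 3 points (85.9 - 83.0) at 1.96.

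**The case against.** A reader might infer that the protocol promises 90% power for the step-down 3.5 mg test. No sentence says so. Section 4.1 speaks of power for one treatment arm against placebo, the 29.1 events are stated for 7.5 mg, and the hypothesis in Section 9.1 names 7.5 mg only. This stands: the fault is an over-broad sizing statement and footnote plus a missing specification, not a false number. *Independent* can also be read as sizing each pair separately; even so, nothing tells the reader that the second pair fares worse.

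A reader might also take 72% as the power. It is the low end, because it needs a boundary that the plan never assigns to 3.5 mg. At 1.96, with 45 total events and futility ignored, power reaches about 90 to 91%. But that case needs more pair events than the 29.1 planned, it uses a critical value that does not hold 2.5%, and 7.5 mg then has about 96% power.

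It is tempting to say that the step-down rule costs almost nothing and the early stop everything, by setting 89.4% (no interims) beside 90.0% (with interims and futility). Those are unlike designs; the like-for-like cost is 4 to 4.5 points.

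Finally, nothing in the documents makes dose selection hinge on 3.5 mg significance. Section 9.5.2.1 gives relapse rates with intervals for every arm, and Section 8.7 brings in pharmacodynamics. That limits the harm but does not supply the missing boundary.

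**Conclusion.** The point holds as a problem of specification and wording. The 90% applies to 7.5 mg versus placebo. For 3.5 mg at 29.1 pair events, power is about 72%, 79% or 83% depending on a boundary that the plan does not give; at the 45-event trigger it is about 76%, 85% or 87-88%. These figures assume hazard ratio 0.272 for both doses, correlation 0.5 and futility obeyed. Equal effect is generous, since Section 4.3 expects 3.5 mg to act at the lower end of the target range; at a hazard ratio of 0.40 the figures fall to 47%, 52% and 60%.

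A reader might conclude that the sample size is wrong. It is not: the 7.5 mg power, the 29.1 events and the 84 participants all stand. Whether 3.5 mg is formally tested at all is also unsettled, because Sections 9.3 and 9.5.2.2 conflict.

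**What to change.** 1. Section 9.2: describe the comparisons as pairwise comparisons sharing one placebo arm rather than as independent. Limit the 29.1 events and 90% power, including footnote a, to 7.5 mg versus placebo. State the power of the step-down 3.5 mg test together with its boundary, event count and assumed hazard ratio.
2. Section 9.3: give 3.5 mg its own one-sided 2.5% alpha-spending function, for example Pocock-type (z = 2.157 at 50% information, 2.201 at the end), and leave the 7.5 mg boundary unchanged. At 29.1 pair events and a hazard ratio of 0.272 this gives about 79% instead of 72%.
3. Reconcile the step-down test in Section 9.3 with the statement in Section 9.5.2.2 that secondary endpoints are not formally tested.

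The cost is wording, with no extra participants or follow-up. The stated power for 3.5 mg becomes less favourable, and under the Pocock-type option its final boundary tightens from 1.969 to 2.201 in exchange for one that is easier to reach at an early stop.
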